4.2 Handling of Dropouts

Annualized number of total bleeds will be calculated for all subjects, including dropouts. See formula in Section 4.5. Subjects who drop from the study will be included in a listing.

4.3 Handling of Missing Data

Each subject's start and stop date will be needed to compute the annualized bleeding rate. If a bleed date is missing, but an infusion date is available, infusion date will be used as the bleed date. Otherwise, use imputation rules as specified in "Analysis Datasets" document.

Missing or incomplete AE start and end date or time: For the purpose of treatment emergent flags, missing AE start day will be imputed as the 15th of the month. However, if the AE start day is missing, but the AE starts during the same month as the first dose, or if the AE starts on the same day as the first dose, but the AE start time is missing, the AE start day (and time in the

second case) will be taken from first dose start day (and time). If both day and month of AE start date are missing, day and month will be imputed as July 1st, or the date of the first dose, whichever comes later.

Drug-related AE tables will include AEs with missing values of causality.

Imputation rules for AE durations (days) are described in the analysis datasets specifications.

When computing age at diagnosis, age at start of therapy, and time since start of therapy; if day is missing, use 15. If month and day are missing, use July 1. If necessary, adjust imputed dates so they are not before the birth date.

4.4 Interim Analyses and Data Monitoring

The trial data will be reviewed periodically by an independent Data Monitoring Committee (DMC). The DMC will review certain safety and efficacy data sets as defined in the charter, as well as the planned interim analysis, and provide written reports to the sponsor. The decision to open enrollment to each age group will be made following recommendation of the DMC.

Although not considered an interim analysis, the 6-month data for PTPs will be analyzed for regulatory purposes as a final analysis of the main study. Safety will be assessed in 10-20 PTPs before enrollment of PUPs begins.

4.5 Data Rules

All bleed and infusion data will be entered into the EPD (hospital infusions will be entered into an eCRF) and imported into SAS. If an infusion is given for a bleed and the bleed information is not provided, the infusion date will be used as the bleed date. Total bleeds is the sum of spontaneous bleeds, trauma bleeds, untreated bleeds, and 'other' bleeds. Bleeds occurring before start of prophylaxis treatment with study medication will not be counted.

Bleeding rate will be annualized using the following formula:

Annualized bleed rate under prophylaxis =

```
(number of bleeds) * 365.25 / (last datetime in study – 1st datetime in study) / (60*24)
```

where:

- 1st datetime in study is the datetime of the first prophylaxis dose (usually Visit 2)
- last datetime in study is the later of the date of Visit 6 (assume time of visit is noon) or last datetime in the EPD prior to the extension period.

Prophylaxis infusions per week will be defined using the following formula:

Number of prophylaxis infusions per week =

(number of prophylaxis infusions) / (last date time in study – 1st date time in study) / (60*24*7) "24 hour rule": Count no more than 1 bleed in a calendar day. If there is more than 1 bleed in a calendar day, to determine the bleed that gets counted, give priority to treated bleeds, spontaneous or trauma bleeds, then joint bleeds. Otherwise, count the first bleed in the day. Severity and treatment response will come from this selected bleed. Bleed site will be aggregated over all bleeds from that day. Regardless of which bleed is selected, the time of the first bleed in the day will be used. All other infusions in the day for treating bleeds will be considered follow-up infusions.

"72 hour rule": Do not count a spontaneous joint bleed or muscle bleed if it occurs within 72 hours of a bleed at the same site. [For a bleed to be affected by this rule, all sites listed on the bleed must also be specified in the previous bleed. If the current and previous bleeds are both skin/mucosa bleeds, this rule does not apply.] Such infusions for bleeds will be considered to be follow-up infusions.

When sorting the infusion records for counting number of infusions associated with each bleed, 1st infusions for bleeds will use the bleed date (if missing then use the infusion date). Follow-up infusions will use the dose date.

Joint bleeds can occur in more that 1 joint site. For each joint bleed, count all sites (combining left and right). For the table showing the Joint Site frequency, sum counts over all sites.

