7.3 Efficacy

7.3.1 Efficacy variables

The primary variable is the annualized number of **total bleeds (sum of spontaneous bleeds and traumatic bleeds) during prophylaxis that occurs** within 48 h **of the last prophylaxis infusion. Both joint and non-joint bleeding will be assessed. (as of Amd 1)** Additional efficacy parameters include:

- Subject/parents' assessment of the response **to** treatment of bleeding events, which is assessed as excellent, good, moderate or **poor. (as of Amd 1)**
- Annualized number of **total bleeds (sum of spontaneous and trauma bleeds) (as of Amd 1)** during prophylaxis treatment
- Assessment of **adequacy of hemostasis (as of Amd 1)** during surgical interventions
- Number of infusions for the treatment of a bleed
- Consumption of FVIII

The main surrogate efficacy parameter is the **recovery of FVIII after infusion. (as of Amd 1)**

If an infusion is given to control a bleed at the same location within 72 hours of the previous dose for a bleed at that site, it is to be considered a follow-up infusion and not treatment of a new bleed, unless both bleeds are skin/mucosa bleeds (as of Amd 3).

The complete list of variables to be analyzed for this study will be provided in the Statistical Analysis Plan.

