7.3.2.2 Treatment logs / bleeding verification

Treatment (as of Amd 1) logs are commonly used for hemophilia subjects for documentation of their home treatment. Home treatment and bleeding frequency are key variables evaluated in this study. Study specific logs will be provided in national language. The preferred system for this study will be EPD devices since they are interactive, allow for real time data transmission, record-stamp date and time of fulfillment and facilitate the clarification of data with the site and also the data cleaning process.

Subjects/parents/caregivers will be provided with EPDs for the whole study. At Screening and Baseline visits, subjects and parents/caregivers will be trained in the use of the device. These logs will be used to collect the *treatment (as of Amd 1)* data and bleeding episodes by the parents/caregivers or subjects, and interact on a *regularly scheduled (as of Amd 1)* basis with the investigator or delegate to verify and complete the *data on (as of Amd 1)* the EPD. Thus, the EPD will be considered the source for these data.

For each *use* of study medication including the *infusions* administered during a planned visit for evaluation of recovery, information must be recorded on the *Treatment (as of Amd 1)*

Logs as follows:

1. Date and time
2. Lot numbers / number of vials administered

3. Reason for *treatment (as of Amd 1)* (prophylaxis, spontaneous bleed first treatment, trauma bleed first treatment, follow-up treatment, surgery, other). ***(If an infusion is given in response to a fall or identified trauma, such as may occur when a child has an uncomplicated blow to the head and there is no clinical sign or evidence of bleeding, the event should be recorded as prophylaxis.) (as of Amd 1)***

If treatment is for a bleeding episode: site of bleeding, severity (severe, moderate, mild), and response to treatment (excellent, good, moderate, *poor, too early to tell*) ***are to be recorded. If 'too early to tell' is entered, the subject will be queried for a response the next time they use the device. For guidance to the subject or their caregivers, the following definitions for response to treatment are suggested. Individual subject responses may vary (as of Amd 1):***

- ***Excellent: Abrupt pain relief and /or improvement in signs of bleeding with no additional infusion administered (as of Amd 1)***

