4.1 General Principles

The statistical evaluation will be performed by using the software package SAS release 9.2 or higher (SAS Institute Inc., Cary, North Carolina, United States). All data will be listed and summary tables will be provided. The number of data available and missing data, mean, standard deviation, and other summary statistics will be calculated for continuous data. Frequency tables will be generated for categorical data. Unless otherwise noted, any statistical tests will be 2-sided and performed at the 0.05 significance level.

Standard programs such as ADMAP and MOSTO will be used.

There will be a Validity Review Meeting and it is possible that this SAP might be updated based on the Validity Review Report.

The primary variable is the annualized number of total bleeds (sum of spontaneous bleeds, trauma bleeds, untreated bleeds, and 'other' bleeds) that occur within 48 hours after all prophylaxis infusions. [Note this is a change from the protocol that defined total bleeds to be the sum of spontaneous bleeds and trauma bleeds.]

Secondary efficacy parameters are:

- Annualized number of total bleeds (sum of spontaneous bleeds, trauma bleeds, untreated bleeds, and 'other' bleeds) during prophylaxis treatment
- Hemostatic outcome of surgeries (both major and minor) including blood loss, transfusion, and/or hemostatic-related surgical complications
- FVIII recovery values
 [note: recovery = (post-infusion FVIII pre-infusion FVIII) * body weight / IU]

Additional efficacy parameters are:

- Annualized number of joint bleeds, spontaneous bleeds, and trauma bleeds that occur within 48 hours after all prophylaxis infusions
- Annualized number of joint bleeds, spontaneous bleeds, and trauma bleeds

- % of joint bleeds in target joint for subjects with target joint
- Number of infusions for the treatment of bleeds per bleed
- For all infusions and prophylaxis infusions, FVIII usage calculation expressed in number of infusions, IU, IU/kg, IU/infusion, IU/year, IU/kg/infusion, and IU/kg/year.
- For bleed infusions, FVIII usage calculation expressed in number of infusions, IU, IU/bleed, IU/kg/bleed, IU/bleed (first infusion), IU/kg/bleed (first infusion), IU/infusion, IU/year, IU/kg/infusion, and IU/kg/year.
- For surgery infusions, FVIII usage calculation expressed in number of infusions, IU, IU/kg, IU/infusion, and IU/kg/infusion.
- Description of bleeding according to type, severity, and location as indicated on EPD

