'other' bleeds # untreated bleeds if subject has a target joint, % of joint bleeds in target joint exposure days [number of different calendar days with at least one infusion] number of infusions/subject total dose (IU) total dose per kg (IU/kg) total dose per kg per year (IU/kg/year) dose per infusion (IU/kg/infusion) total dose per infusion (IU/infusion) total dose per year (IU/year). number of prophylaxis infusions/subject total dose for prophylaxis (IU) total dose for prophylaxis per kg (IU/kg) prophylaxis dose per year (IU/kg/year) dose per prophylaxis infusion (IU/kg/infusion) total prophylaxis dose per infusion (IU/infusion) total prophylaxis dose per year (IU/year) number of infusions for bleeds Total dose for bleeds (IU) Total dose per bleed (IU/bleed) First dose per bleed (IU/kg/bleed) Total dose per kg for bleeds (IU/kg) Total dose per kg per bleed (IU/kg/bleed) Total dose per kg per spontaneous bleed (IU/kg/bleed) Total dose per kg per trauma bleed (IU/kg/bleed) Total dose per year for bleeds (IU/year) Total dose per infusion for bleeds (IU/inf) Dose per infusion for bleeds (IU/kg/inf) Dose per year for bleeds (IU/kg/year) number of infusions for surgery Total surgery dose (IU) Total surgery dose per kg (IU/kg) Total surgery dose per infusion (IU/inf) Dose per surgery infusion (IU/kg/inf) **Bleed level dataset (ADCE):** One record per bleed per subject:

indicator variable: bleed treated (no/yes) indicator 1st bleed since most recent prophylaxis infusion (no/yes) number of infusions number of infusions (0, 1, 2, 3, 4, >4) number of infusions (<=2, >2) **Statistical Analysis Plan**

reason for 1st infusion (spontaneous, trauma, other, missing) type of bleed (joint, muscle, skin/mucosa, internal, other) if joint bleed and subject has a target joint,

indicator variable: bleed in target joint or bleed not in target joint response to treatment (poor, moderate, good, excellent) bleed severity (mild, moderate, severe) time from this bleed to 1st infusion for this bleed (hours) time from last prophylaxis infusion to this bleed (days) time from last prophylaxis infusion to this bleed (<1, 1-2, 2-3, 3-4, 4+ days) indicator variable: bleed within 48 hours after most recent prophylaxis infusion time from last infusion to this bleed (days)

Infusion level dataset (ADEX):

One record per infusion per subject:

indicator variable: drug used was study drug (no/yes)

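### Part A SAP 4.5 attaches follow-up infusions to bleeds by position in a list sorted on two different clocks, so overlapping bleeds can get wrong infusion counts; the effect is small and confined to descriptive bleed-level outputs

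*SAP*

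**What the plan says.** Among its additional efficacy parameters, Part A SAP 4.1 lists "Number of infusions for the treatment of bleeds per bleed". Section 4.5 gives the ordering used to obtain it. The rule opens "When sorting the infusion records for counting number of infusions associated with each bleed" and continues "1st infusions for bleeds will use the bleed date (if missing then use the infusion date). Follow-up infusions will use the dose date". First infusions are thus placed at the time of the bleed, and follow-ups at the time of the dose.

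The SAP does not say in words how a follow-up is then matched to a bleed. In the example in 6.2.1, record 4 is a bleed, record 5 is a follow-up, and the bleed in record 4 is given two infusions. That is attachment to the preceding bleed record. Neither SAP v2.1 nor its 2013 supplement mentions matching by site or by a bleed identifier.

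Two other rules in 4.5 create follow-ups. The 24 hour rule keeps one bleed per calendar day and turns the day's other bleed infusions into follow-ups; for the bleed that is kept, "Regardless of which bleed is selected, the time of the first bleed in the day will be used". The 72 hour rule turns the infusion for an early spontaneous joint or muscle re-bleed at the same site into a follow-up.

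Protocol 7.3.1 defines a follow-up by location: an infusion for a bleed at the same site within 72 hours of the previous dose, where "it is to be considered a follow-up infusion and not treatment of a new bleed" (skin and mucosa bleeds excepted). Under protocol 7.3.2.2 the diary records "site of bleeding, severity (severe, moderate, mild), and response to treatment".

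**The concern.** The stated purpose of the sort is to count infusions per bleed, so the sort key determines the counts. A newer bleed enters the list when it starts, not when it is first treated. If a follow-up for an older bleed falls between those two times, it sits below the newer bleed and is counted there. The older bleed is then one short, and the newer one gains an infusion given before its own treatment began.

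Gaps between bleed and first infusion are expected: 6.2.1 derives that interval in hours for each bleed, and 6.2 correlates it with severity and with response. The affected count feeds infusions per bleed, the split at two infusions, dose by bleed (including dose per spontaneous and per trauma bleed), and the Spearman correlations of number of infusions with severity and with response.

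**Working it through.** **1. The SAP's own example.** Coding the 4.5 sort and giving each follow-up to the nearest first-infusion record above it reproduces 6.2.1: one infusion for the joint bleed, two for the muscle bleed, and 2 × 365.25 / 182 = 4.01 bleeds a year. The example has no overlapping bleeds, so it does not test the rule.

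**2. Constructed sequences** (times in hours; A is the older bleed, B a newer bleed at another site, Z an unrelated bleed more than a week before).

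| Case | True count | SAP key | All records on dose time |
|---|---|---|---|
| A bleeds 8, infused 10, follow-up 40; B bleeds 32, first infused 50 | A=2, B=1 | A=1, B=2 | A=2, B=1 |
| Same, with an extra follow-up for A at 22 | A=3, B=1 | A=2, B=2 | A=3, B=1 |
| A as in row 1; B bleeds 32, infused 33 | A=2, B=1 | A=1, B=2 | A=1, B=2 |
| 24 hour rule: counted bleed A timed 8, infused 14; another infusion at 10 relabelled follow-up | Z=1, A=2 | Z=1, A=2 | Z=2, A=1 |

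Row 1 is the mixed-key error. In row 2 it moves the share of bleeds with two or fewer infusions from 1 of 2 to 2 of 2. Row 3 is an error of order-only attachment, and both keys make it. In row 4 the SAP key is right and dose-time sorting is wrong.

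The general condition, for two bleeds treated in the order they occur, is as follows. The SAP key misplaces a follow-up for A given after B *starts*. Dose-time sorting misplaces one given after B is *first infused*. The mixed key is therefore responsible only for follow-ups falling between those two times.

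**3. Frequency.** The documents supply no rates or delays, so these are assumptions: 4 or 12 bleeds per child-year at random times; exponential delay to first infusion with mean 6, 12 or 24 h; 40% of bleeds with one or two follow-ups at 24-hour steps; 20,000 child-years per setting. Percentage of bleeds with a wrong count:

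| Bleeds/year | Mean delay (h) | SAP key | All on dose time | Difference (points) |
|---|---|---|---|---|
| 4 | 6 | 1.56 | 1.34 | 0.22 |
| 4 | 12 | 1.76 | 1.29 | 0.47 |
| 4 | 24 | 2.13 | 1.25 | 0.88 |
| 12 | 6 | 4.47 | 3.87 | 0.60 |
| 12 | 12 | 5.02 | 3.80 | 1.22 |
| 12 | 24 | 6.14 | 3.74 | 2.40 |

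Repeat runs put the SAP-key figure between 1.4% and 6.2% overall, and the difference at about 0.2 to 0.8 points (4 a year) and 0.6 to 2.4 points (12 a year); the last digit is simulation noise. Follow-ups credited to a bleed not yet infused equal about 0.1% to 1.7% of bleeds.

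**4. The split at two infusions.** At 12 a year, the true share with two or fewer is 79.95/79.96/80.12% for the three delays. The SAP key gives 80.45/80.47/80.59%, and dose-time sorting gives the same three figures. The marginal split moves by about half a point (80.45 − 79.95 = 0.50) and the key makes no visible difference to it. Individual bleeds are misclassified more often: 0.8% to 1.1% at 4 a year and 2.3% to 3.2% at 12.

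**5. What cannot move.** Each misplaced follow-up leaves one bleed and joins another in the same child. Total infusions, mean infusions per bleed and a child's average dose over all bleeds are unchanged. The primary variable, annualized bleeds within 48 hours of prophylaxis, does not use this count.

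**6. Linking by site.** With six equally likely sites (an assumption), matching follow-ups to the most recently infused bleed at the same site lowers wrong counts to about 0.2% to 0.7%.

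**The case against.** The strongest reply has three parts.

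First, the attachment rule is inferred. Section 4.5 gives sort keys only, the example has no overlap, and the SAP refers to a separate Analysis Datasets document as an integral part of the plan. That document is not available and may link follow-ups by site. This stands as a limit. It does not rescue the text of 4.5, which states that the sort is for counting and names no other link.

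Second, the bleed-date key has a rationale. Under the 24 hour rule it keeps same-day infusions with the counted bleed, which dose-date sorting can lose (row 4 of the first table). This stands in full. A reader might infer that moving every record to dose date is a free and complete cure. It is not: it brings in that new error and leaves row 3 uncorrected.

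Third, the trigger is narrow and the outputs are minor. The 24 and 72 hour rules remove some overlaps, the parameter is an additional descriptive one in a planned 50 children, and the Part B SAP does not repeat the sort and defines the count as the first infusion plus follow-ups for that same bleed. All of this stands, and it is why the point ranks low.

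**Conclusion.** The point holds as a minor defect. As written, the Part A rule can credit a follow-up to the wrong bleed when bleeds overlap, including a bleed not yet infused. Under the stated assumptions about 1.4% to 6.2% of bleeds would carry a wrong count. Clustered bleeding would probably raise this, and less overlap would lower it.

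Stronger readings are not supported:

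- A reader might attribute the whole 1.4% to 6.2% to the mixed sort key. Sorting on dose time alone leaves about 1.2% to 3.9%, so at least three-fifths of the error in the table above (3.74 of 6.14 in the worst setting) comes from attaching by order.
- A reader might infer bias in the primary efficacy result or in mean infusions per bleed. Neither can change.
- A reader might infer that the planned correlations are materially weakened. They rest on bleed-level pairs that can be wrong, but the effect on them has not been calculated.

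**What to change.** In Part A SAP 4.5, replace attachment by sort position with an explicit link:

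1. Link each follow-up to its bleed by recorded site or diary identifier, in line with the same-location definition in protocol 7.3.1.
2. Link an infusion relabelled as a follow-up by the 24 hour or 72 hour rule to the bleed it was merged into.
3. Only where neither link exists, attach the follow-up to the most recently infused bleed by dose date and time.
4. Apart from infusions relabelled under step 2, never credit a follow-up to a bleed whose first infusion is later.

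The bleed date can still be used to time the bleed itself.

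The cost is a few sentences and a slightly more complex derivation, using data the diary already collects. The Analysis Datasets document has to be checked and aligned; if it already contains such a link, 4.5 should say so. The Part B SAP describes the Part A analysis as complete and reported, so the practical use is a check on the tables already produced and a settled rule for the overall final analysis.

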4.6 Validity Review

Final decisions regarding validity will be made during the Validity Review Meeting and documented in the Validity Review Report. Any changes to the statistical analysis prompted by the results of this review meeting will be documented in an amendment and, if applicable, supplement to this SAP.

5. Analysis Sets

5.1 Assignment of analysis sets

The safety analysis set (SAF) will include all subjects who were entered into the study and received study drug. The intent-to-treat analysis set (ITT) will include all subjects in the SAF who have infusion/bleeding data from the EPD. The per-protocol analysis set (PPS) will include all ITT subjects who have no major protocol deviations and have EPD data. The ITT will be used for the primary efficacy analysis. The efficacy analysis of the PPS will be considered supportive. Data from Part B and the extensions will be summarized separately.

Specific rules for major protocol deviations will be documented in the "Protocol Deviations Document" (PDD) prior to validity review meeting. Final decisions regarding the assignment of subjects to analysis sets will be made during the Validity Review Meeting and documented in the Validity Review Report.

Subjects will be excluded from the PPS for non-compliance if they violate any of the following criteria (for PTPs only):

- at least 1 interval between all infusions > 30 days
- at least 2 intervals between all infusions > 21 days
- at least 3 intervals between all infusions > 14 days
- number of infusions < 80% number of expected infusions [use expected number of infusions = (prescribed number of infusions per week) * (last datetime in study 1st datetime in study) / (60*24*7)]
- at least 20% of prophylaxis infusions at a dose level < 15 IU/kg (for PTPs)
- at least 20% of prophylaxis infusions at a dose level < 10 IU/kg (for PUPs) [Note: not applicable to this SAP)

All tables will summarize data with columns for PTP 0-<6 years, PTP 6-12 years, and Total.

Pharmacokinetic Analysis Set

All subjects with evaluable PK-data will be included in the analysis of pharmacokinetic data.

Subgroups:

Subgroup tables will be provided. Possible subgroups for number of bleeds within 48 hours after prophylaxis per year and number of bleeds per year to be presented are:

- Prophylaxis Treatment regimen (<=2x/week, >2x/week)
- Average prophylaxis dose high (>=30 IU/kg), low dose (<30 IU/kg)
- Average prophylaxis dose/week high (>=80 IU/kg), low (<80 IU/kg)
- prior treatment (on-demand, prophylaxis)
- Race Group (white, non-white)
- Region (North America, Europe, Israel)
- Number of Bleeds during previous 12 months (<median, >=median)
- Number of Joint Bleeds during previous 12 months (<median, >=median)
- Presence of Target Joint (no, yes)

6. Statistical Methodology

6.1 **Population characteristics**
